Judgment criteria	
The main judgment criterion for the HR will be the evaluation of the concordance between the measurements obtained following the application of the reference technical processes of non-operator dependent measurement taking via a CE marked device and via COBOX.
 
The secondary judgment criterion associated with the measurement of the RR will also be the subject of an evaluation of the concordance between the measurements obtained via a reference method of manual counting

	
according to the good practices of the medical or paramedical nursing staff (or arc or tec) and via COBOX.
 
For each of the parameters measured, we will establish the repeatability of the measurement and its accuracy (comparison of the relative error expressed as a percentage between the two types of measurement).

Study size	323 patients
Planned number of centers	4
Search duration	
Duration of participation for each patient: less than 30 minutes
 
Total research duration: 3 months
 
Approximate study start date: mid-July 2022
 
Approximate study end date: mid-October 2022

Statistical analysis of data	
The performance of the tool will be estimated by the concordance between the measurements obtained from the application of the reference technical process via a CE marked device and with the measurements obtained by COBOX.
 
An intraclass correlation coefficient (ICC) with its 95% confidence interval (95% CI) will be calculated. Measurement errors will be calculated and expressed as a percentage (root mean square error, etc.).
 
The two study samples will be compared by Student's t test and Fischer's F, with a desired significance for P value = 0.05, for all the analyses.
 
A DIXON test will be performed to assess the presence of statistically outliers within the samples.

Expected benefits	
These data will enable the COBOX tool, a class IIA medical device, to be validated in terms of measurement performance compared to a CE-marked device used in a reference technical process for taking measurements and a reference method for manual counting. Applications for taking constants without contact have a wide field of application in

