COBOX is a tool for measuring cardiac and respiratory rhythm in routine clinical practice for patients outside intensive care and outside continuous monitoring. We expect a correlation coefficient of more than 0.7 between the COBOX measurements and those obtained using the reference method. Regarding the secondary endpoints, we expect average standard deviations

between COBOX and the reference methods of 5 bpm for the heart rate and 3 bpm for the respiratory rate.

Expected benefits

These data will validate the COBOX tool in terms of measurement performance compared to the results obtained through the application of reference processes for taking measurements using CE marked devices, as well as those obtained using the reference method of counting manual. Applications for taking physiological constants without contact have a wide field of application in the field of routine care and save medical time, increase quality by limiting manual copying errors and the risk of contamination.

6. Research design

Research scheme

This is an observational study, responding to Article 62.1 of the European medical device regulations, prospective, comparative.

Primary endpoint

The main judgment criterion will be the intra-class correlation coefficient between the measurement by COBOX and the measurement obtained thanks to the application of the reference processes for taking measurements via a measurement by a CE marked tool (for HR).

In order to ensure the repeatability of the device, three successive comparative measurements (each spaced 5 seconds apart) on the same patient will be carried out.

Secondary endpoints

The additional secondary judgment criteria will be:

- For RF (ranked criterion): comparison with a manual measurement following a reference method of manual counting according to good training practices for healthcare personnel trained in taking measurements (ide, as, internal external).
- The reliability of the reproducibility of the measurement
- The time in seconds dedicated to taking the parameters with and without the COBOX tool (time for installing and removing the tool if applicable, time for completing the medical file if applicable, effective time for taking the HR constants and FR).
- Assessment of treatment costs:
 - Pick-up times / delays
 - Total treatment costs (direct medical and non-medical costs)

Inclusion criteria

- Adult patient (18 years and over)
AND
- Patient consulting in the emergency department of a participating center
AND

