- Patient having constant FC and FR taken by the nursing staff (or arc or tec) of emergency reception
AND
- Patient who did not express his opposition to participate in the study
AND

- Patient affiliated to a social security scheme

Non-inclusion criteria

- Patient in a state of vital emergency with direct entry into SAUV or intensive care.
- Patient unable to express consent.
- Patient unable, for health reasons, to face the COBOX tool.
- Patient unable to stand for 30 seconds facing the COBOX solution.
- Patient with skin stigma over more than 50% of the face (burn, graft)
- Patient with the face covered or not allowing access to the entire face (clothing)

Recruitment methods

In order not to delay the care of patients in the emergency room, recruitment is carried out by the IOA (or arc or tec) at the time of their usual care. She communicates oral information to the patient on the use of the tool during the measurements and presents the consent letter in electronic format in the tablet. If the patient gives consent, the test is performed. In case of opposition, the COBOX device will not be used.

It is therefore a serial recruitment, without selection of the participants.

7. Experimental device(s) and comparator(s)

Description of exposure to comparators

In order to standardize the measurements of the four hospital centers, QUANTIQ will provide each center with a CMS60D digital pulse oximeter from the Contec brand. This device is CE marked and commonly used in hospitals. This device will be used at the same time as the CE marked device used during the reference technical process of the hospital center, without modifying the practices of each center. The comparison of results will be between the Contec CMS60D and the COBOX tool.

Device	Acquisition cost	Trolley (300 to 700 Euros)	Whip Set and Monobase Cables	Lifespan (Year)	Annual Maintenance Cost	Annual cost for 1 technical platform
Contec CMS60D Digital Pulse Oximeter (SpO2 - Heart Rate)	242.50 €	N / A	N / A	2 YEARS (AVERAGE)	Replaced/No Maintenance - PURCHASE Management (12.1 €)	133.4 €

List of any other medical device or drug that will be used during the clinical investigation.

The Contec CMS60D reference DM will be provided by Quantiq while COBOX will be installed on a Samsung S6 tablet also provided by Quantiq.

Number of experimental devices to be used, along with a rationale

3 reference Contec CMS60D oximeters will be provided per center.

Treatment(s)/ management of experimental devices

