
QUANTIQ provides users with one tablet per site per physician. Delivery of a functional tablet in the event of a malfunction within 5 working days. Bug fix within 3 days in case of software malfunction with continuous information for professionals.

8. Research process

Research timeline

- Start of inclusions: Mid-July 2022
- Duration of the inclusion period: 2 months
- Duration of participation of each patient: The time of their passage in the IOA box (less than 30 minutes)
- Total research duration: 3 months

Summary of patient follow-up

- Oral information by the IOA. If necessary, an investigating physician can complete the information at the patient's request.
- Informed consent with electronic signature.
- Collection of the patient's age, gender and Fitzpatrick phototype.
- Collection of patient identification number.
- The nursing staff (or arc or tec) installs the oximeter on the patient's finger.
- The nursing staff (or arc or tec) starts COBOX and begins to count the breaths in parallel.
- After 15s, a first measurement is made by COBOX. The pulse oximeter reference result is acquired in parallel, associated with the patient ID number and stored with the COBOX result at the same time on an electronic database.
- After 20s (5s after the previous measurement), a second measurement is made by COBOX. The pulse oximeter reference result is acquired in parallel, associated with the patient ID number and stored with the COBOX result at the same time on an electronic database.
- After 25s (5s after the previous measurement), a third measurement is made by COBOX. The pulse oximeter reference result is acquired in parallel, associated with the patient ID number and stored with the COBOX result at the same time on an electronic database.
- After 30s, the nursing staff (or arc or tec) enters the number of breaths counted since the start. This result is converted into a respiratory rate (RR) then associated with the patient number and stored in the database.

The data is blocked on the database until the end of the study. At the end of the study, they will be sent to the coordinating centre.

In order not to disrupt the general operation of the emergency department and patient care, the usual patient circuit is not modified. The COBOX tool is used by the reception staff in a contemporary way to their usual collection of input parameters.

Collection of consent

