10. STATISTICAL ASPECTS

Study size calculation

Considering the results of the performance verification tests of the medical device under study, we have established the study hypotheses in connection with the calculation of the size of the study set out below:

Minimum acceptable value of the ICC correlation coefficient (ρ_0)	0.6
Expected value of the ICC correlation coefficient (ρ_1)	0.7
The number of observations per subject k	3
Two-sided significance level (α)	0.05
Power (1 - β):	90%
Minimum size (n)	226
Size at 30% safety margin	323

A final study size of 323 patients is retained; taking into account a rate of unusable data of 30% in order to maintain the statistical power of the study in the event of exclusion of outliers.

Statistical methods used

The analysis will carry an initial descriptive part. The qualitative variables will be expressed in frequencies (with their 95% CI), and the quantitative variables expressed in means (with their standard deviation) if the distribution is normal. Otherwise, the quantitative variables will be expressed as the median (with their interquartile range).

Then, we will perform a comparative analysis, using chi 2 tests (or Fisher's exact) for the qualitative variables and student test (or Mann-Whitney test if applicable) for the quantitative variables. For performance estimation, we will determine the intra-class correlation coefficient with its confidence interval and we will perform a graphical analysis of Bland and Altman. In addition, we will calculate the mean square errors between the measurement with COBOX and the reference measurements, and they will be expressed as a percentage.

All our analyzes will be carried out at the 5% significance level.

An analysis of the repeated and compared measurements between COBOX and the CE marked device (used during the technical reference process for taking measurements) for the heart rate will make it possible to evaluate the reproducibility of the COBOX on repeated measurements in the *COBOX Protocol Valid*

same individual. A secondary statistical analysis will be done for the measurement times T+5s and T+10s.

We will use imputation methods or sensitivity analysis for the management of missing data.

11. Access rights to source data and documents

Access to data

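### The three COBOX readings come from one start of the device, so they show stability within a recording and cannot support the planned repeatability and reproducibility claims

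*Combined protocol and SAP*

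**What the plan says.** All references are to the combined protocol and SAP.

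- **Purpose.** Section 6 (Primary endpoint) ties repeatability of the device to three readings: "three successive comparative measurements (each spaced 5 seconds apart) on the same patient will be carried out". Section 1 (Judgment criteria) promises, for each parameter measured, that "we will establish the repeatability of the measurement and its accuracy". Section 5 lists repeatability among the secondary objectives for both heart rate (HR) and respiratory rate (RR). Section 6 (Secondary endpoints) adds the reproducibility of the measurement.
- **Procedure.** In Section 8 (Summary of patient follow-up) the operator "starts COBOX and begins to count the breaths in parallel". Then: "After 15s, a first measurement is made by COBOX"; "After 20s (5s after the previous measurement), a second measurement is made by COBOX"; "After 25s (5s after the previous measurement), a third measurement is made by COBOX". The oximeter value is stored alongside each reading. No stop, restart or repositioning is described between readings.
- **Analysis.** Section 10 says that comparing the repeated HR measurements with the reference device "will make it possible to evaluate the reproducibility of the COBOX on repeated measurements" in the same individual. It also plans a secondary analysis at T+5 s and T+10 s. It makes no allowance for signal shared between readings.
- **Related limit.** A non-inclusion criterion in Section 6 reads "Patient unable to stand for 30 seconds facing the COBOX solution", which fits a single short session.

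The length of video behind each reading is not given anywhere.

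**The concern.** A repeatability figure should tell a user how far the answer would move if the measurement were made again. Section 5 places COBOX in routine practice outside continuous monitoring, so making the measurement again means starting the device again. The design never does this. Three values read 5 s apart from one running session share the same face acquisition, camera position and lighting, and probably part of the same video.

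A device that settled on a different value at each start could therefore look highly repeatable in this trial. The report would then carry a repeatability result, and in Section 10 a reproducibility result, that the data cannot establish. This matters most for RR, because Section 3 presents a reproducible and repeatable RR method as one of the product's aims.

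**Working it through.** **The plan's own figure.** The only calculation that uses the three readings is the sample size in Section 10: ρ0 = 0.6, ρ1 = 0.7, k = 3, two-sided α = 0.05, power 90%. With θ = ρ/(1−ρ), θ0 = 1.5 and θ1 = 2.333, so C0 = (1 + 3×1.5)/(1 + 3×2.333) = 5.5/8 = 0.6875. Then n = 1 + 2(1.960 + 1.282)²×3 / [(ln 0.6875)²×2] = 225.5, rounded up to 226, and 226/0.7 = 323. Both stated figures reproduce, and the point below does not concern them.

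**What the three readings can contain.** Write reading j on patient i as true rate + b_i + e_ij, where b_i is the error specific to that start of the device. Between separate starts the error variance is σ_b² + σ_e². Among three readings from one start, b_i is common and cancels. The expected within-patient variance, once true change is removed, is (mean variance of e) − (mean covariance of e). σ_b² is absent whatever the algorithm. It still enters the COBOX-minus-oximeter differences, where it cannot be separated from patient-specific bias.

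**Shared video.** Readings end at 15, 20 and 25 s. For a sliding window of L seconds, neighbouring readings share max(0, 1 − 5/L) of their video, and the first and third share max(0, 1 − 10/L).

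| Assumed window | Neighbouring readings | First and third |
|---|---|---|
| 5 s | 0 | 0 |
| 7.5 s | 33% | 0 |
| 10 s | 50% | 0 |
| 12 s | 58% | 17% |
| 15 s | 67% | 33% |
| Cumulative from start | 15/20 = 75%, 20/25 = 80% | 15/25 = 60% |

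Three separate 15 s windows need 45 s, but the last reading is at 25 s. A window of 5 s or less is hard to square with the plan. The first reading waits 15 s. A 5 s record resolves 60/5 = 12 bpm (15 s: 4 bpm) against the 5 bpm HR standard deviation expected in Section 5. At 12 breaths per minute, 5 s holds one breath; at 20 per minute, 1.7. Overlap is therefore likely, but it is an inference.

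**Effect on the SD (illustration).** Let R be the within-patient SD from the three readings divided by the SD of separate recordings, leaving out start-to-start variation. Errors are assumed independent over time.

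*Model A: each reading averages the error over its window.*
- 15 s sliding: correlations 2/3, 2/3 and 1/3, mean 5/9. R = √(1 − 5/9) = 0.67.
- Shorter sliding windows: 0.75 (12 s), 0.82 (10 s), 0.88 (7.5 s), 1.00 (5 s).
- Cumulative: relative variances 1, 0.75, 0.60; covariances 0.75, 0.60, 0.60. Mean difference 0.783 − 0.650 = 0.133. R = √0.133 = 0.37 against separate 15 s recordings, or √(0.133/0.783) = 0.41 against separate recordings of matching lengths.

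*Model B: each reading is a frequency, estimated as the slope of signal phase on time.* For windows shifted by a fraction x of their length, the correlation is 1 − 3x + 2x³.
- 15 s sliding: x = 1/3 gives 0.074 and x = 2/3 gives −0.407. Mean (2×0.074 − 0.407)/3 = −0.086. R = √1.086 = 1.04.
- 10 s sliding: x = 1/2 gives −0.25 and x = 1 gives 0. Mean −0.167, R = √1.167 = 1.08.
- Cumulative: relative variances 1, (15/20)³ = 0.422, (15/25)³ = 0.216; covariances 0.422, 0.216, 0.216. Mean difference 0.546 − 0.285 = 0.261. R = √0.261 = 0.51 against separate 15 s recordings, or √(0.261/0.546) = 0.69 against matching lengths.

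The same schedule thus gives R from about 0.37 to about 1.0, or slightly above, according to assumptions that the documents do not settle.

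**The case against.** The strongest reply is that repeatability is by definition assessed over a short interval under unchanged conditions, so the same patient, camera position and lighting are not a defect. Each reading is also paired with its own oximeter value, and Section 10 treats the later time points as a separate secondary analysis. This stands in part. Unchanged conditions are proper for repeatability, but the measurement itself must still be repeated, and here successive outputs are read from one run. The reply gives no support to the reproducibility wording in Sections 6 and 10, since no condition changes within a patient. The four centres do not help, because Section 10 refers to repeats in the same individual.

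A reader might infer more than the documents support:

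- *That COBOX needs 15 s of signal, so the readings certainly reuse most of the video.* Section 8 says only when the first reading is made. The delay could include face acquisition or settling.
- *That the repeatability error is understated by a known percentage.* Under Model B a 15 s sliding window shows no understatement, so neither direction nor size is established for the overlap alone.
- *That each later RR reading adds only one breath.* This holds near 12 breaths per minute, which Section 4 gives as the edge of a risk zone, not as a limit of the study population. Section 10 also specifies its repeated-measurement analysis for HR only, although Sections 1 and 5 include RR.
- *That the primary HR agreement result or the sample size fails.* Neither is shown.

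**Conclusion.** The point holds, with moderate confidence. It rests on the procedure as written: one start per patient and three readings within 25 s. Start-to-start variation is not sampled, no other part of the plan supplies it, and reproducibility cannot be evaluated from these data. That conclusion needs no assumption about the algorithm.

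Shared video is likely but conditional: it occurs for any window longer than 5 s. Its effect on the within-patient SD is a range for illustration (ratio about 0.37 to about 1.0) resting on assumed windows, two simple error models and errors independent over time. It should not be quoted as an estimate of bias. Any start-to-start error would come on top, and its size is unknown.

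What changes is the claim the trial may make. The HR comparison with the oximeter, and the figures of 226 and 323, are not put in question by this point.

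**What to change.** **Main change.** In Sections 1, 5, 6 and 10, describe the analysis of the three readings as *stability of successive outputs within one 25 s recording*. Make no repeatability or reproducibility claim from them. State in Section 8 the length of signal behind each reading and whether the window slides or accumulates. This costs wording and one technical statement from the sponsor; data collection does not change.

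**Alternative, if a repeatability claim is wanted.** Keep the 15 s reading for the HR comparison, and compute repeatability from separately started COBOX recordings with the oximeter left in place and read at the end of each. Two further 15 s recordings add 30 s, and allowing up to 15 s for restarts (an assumption) gives about 30 to 45 s more per patient, within a participation time of under 30 minutes. The drawbacks are possible true HR change between recordings and a longer time facing the device. Three 15 s recordings take at least 45 s, which must be reconciled with the 30 s standing criterion in Section 6 and the 30 s breath count in Section 8. Restarts would support repeatability only; a reproducibility claim would also need a condition, such as operator or tablet, to be varied within patients.
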